I agree that all information provided to me by the NIH including protocols, verbal and written information shall be kept confidential and restricted to the personnel involved in conduct of the trial. It is recognized that this information may be conveyed to the IRB/EC. I also understand that reports or information about the trial and its progress shall not be provided to anyone not involved in the trial other than the NIH or other legally constituted authority. The described study will be conducted in compliance with the protocol, clinical practice standards, associated federal regulations, and all University of Pennsylvania research requirements will be followed. Specifically: 45 CFR 46, 21 CFR Parts 50, 54, 56, and 812 and Good Clinical Practice: Consolidated Guidelines approved by the International Conference on Harmonization (ICH).

Clinical Study Number:	NCT06154265	Document Title:	10/24/2024	Page 6 of 36
		Default vs As-Needed Intraoperative Transesophageal Echocardiography (TEE) in Low-Risk Isolated Coronary Artery Bypass Graft (CABG) Surgery: A Randomized Controlled Trial		

3 Protocol Synopsis

Title	Default vs As-Needed Intraoperative Transesophageal Echocardiography (TEE) in Low-Risk Isolated Coronary Artery Bypass Graft (CABG) Surgery: A Randomized Controlled Trial
Overview	The proposed study protocol will randomize low-risk isolated CABG surgery patients to receive either default or as-needed intraoperative TEE. Trial outcomes will include absolute recruitment rate, intervention fidelity, and incidence of gastroesophageal injury.
Primary Objectives	
Primary objectives:
 
 1. Recruitment feasibility assessment as measured by an absolute recruitment rate. Absolute recruitment rate is defined as the number of successfully enrolled participants divided by the total number of screened participants. 2. Assess intervention fidelity by calculating the rate of TEE performed among participants randomized to the as-needed TEE trial arm.
Secondary Objectives	
Secondary Objectives:
 
 1. Evidence of clinically-significant gastroesophageal dysfunction during hospitalization – either by patient-reported symptoms or by the presence of testing for swallowing difficulty, dysfunction, or upper endoscopy diagnostic procedures. 2. Evidence of end-organ dysfunction based on clinical notes (e.g. “transaminitis,” “acute kidney/renal injury”), and/or laboratory-based evidence of (e.g. liver function tests [LFTs], serum creatinine [Cr], lactate, etc.). 3. Incidence of in-hospital, post-surgical, cardiovascular re-intervention (e.g. return to the operating room for any reason, unplanned or emergency cardiac catheterization post-surgery, or placement on venoarterial extracorporeal membrane oxygenation [VAECMO]). 4. Incidence of all-cause in-hospital mortality
Population	Isolated CABG surgery patients meeting trial eligibility criteria (see inclusion/exclusion), scheduled to undergo surgery at hospitals within the University of Pennsylvania Health System.
Key Eligibility Criteria	In addition to meeting strict inclusion and exclusion criteria, subjects must be willing and capable of providing informed consent and physically capable of performing study related activities.
Site	Hospitals within the University of Pennsylvania Health System

Clinical Study Number:	NCT06154265	Document Title:	10/24/2024	Page 7 of 36
		Default vs As-Needed Intraoperative Transesophageal Echocardiography (TEE) in Low-Risk Isolated Coronary Artery Bypass Graft (CABG) Surgery: A Randomized Controlled Trial		

Study Duration	24 months
Participant Duration	
Active participations: Informed consent duration: approximately 30 – 60 minutes
 
Study duration: 5 days (120 hours) starting with the time of patient enters the cardiac operating room for CABG surgery.
 
Passive participation: Full study duration for the purposes of data acquisition, data cleaning, report generation, manuscript preparation and publication where applicable.
 
Total time: ~24 months

Clinical Study Number:	NCT06154265	Document Title:	10/24/2024	Page 8 of 36
		Default vs As-Needed Intraoperative Transesophageal Echocardiography (TEE) in Low-Risk Isolated Coronary Artery Bypass Graft (CABG) Surgery: A Randomized Controlled Trial		

4 Background Information

There is no randomized evidence to support the use of intraoperative TEE in any type of cardiac surgery. This evidence gap is particularly problematic in isolated CABG surgery for three reasons. First, in contrast to the comparative effectiveness studies that have associated intraoperative TEE with improved outcomes after cardiac valve,^{1, 2} proximal aortic,² observational research comparing clinical outcomes after isolated CABG surgeries with (vs without) intraoperative TEE have been equivocal.³⁻⁵ Second, observational research cannot confirm a causal link between intraoperative TEE and improved outcomes. This is especially problematic in isolated CABG surgery given how TEE is used during surgery. For instance, unlike the direct mechanism by which intraoperative TEE could improve outcomes in valve surgery (e.g. facilitating real-time surgical planning,^{6, 7} confirmation of pre-surgical valve pathology,^{8, 9} or immediate identification and resolution of a technical error in valve surgery and avoiding a return to the operating room),¹⁰ the mechanism by which intraoperative TEE could improve outcomes in isolated CABG surgery is indirect (e.g. hemodynamic monitoring by differentiating between cardiac failure¹¹⁻¹³ and hypovolemia).^{14, 15} Third, while life-threatening complications directly attributable to intraoperative TEE are rare (incidence of esophageal perforation from TEE is 0.01%),¹⁶ gastroesophageal injury from TEE after cardiac surgeries range 0.1% – 4%.¹⁷⁻²⁰ Thus, the true risk vs benefit of intraoperative TEE during isolated CABG surgery is unknown.

The unclear clinical efficacy, unknown real-world effectiveness, and undefined risk-benefit ratio of intraoperative TEE during isolated CABG surgery is an evidence gap that may only be resolved prospectively through randomization. Consistent with this assessment, preliminary qualitative research consisting of semi-structured interviews with cardiac surgeons (including [name], Chief of Cardiac Surgery at Penn Presbyterian Medical Center [PPMC]), suggests that cardiac surgeons believe that intraoperative TEE may expose their routine, lower-risk isolated CABG surgery patients to unnecessary complications related to TEE without a commensurate improvement in outcomes. Thus, this proposed feasibility RCT (pre-approved by [name] to take place at PPMC), will capitalize on this existing clinical equipoise to test the practical feasibility of conducting an RCT by randomizing routine, lower-risk, isolated CABG surgery patients to either default or as-needed intraoperative TEE during surgery.

Clinical Study Number:	NCT06154265	Document Title:	10/24/2024	Page 9 of 36
		Default vs As-Needed Intraoperative Transesophageal Echocardiography (TEE) in Low-Risk Isolated Coronary Artery Bypass Graft (CABG) Surgery: A Randomized Controlled Trial		

5 Product Description

This study proposes randomization of default vs as-needed use of transesophageal echocardiography (TEE) –a legally marketed, imaging device that is used intraoperatively during cardiac surgeries in the University of Pennsylvania Health System (UPHS).. The Office of Clinical Research (OCR) has determined that the ultrasound system (probes and machines) proposed for this trial meets the requirements for Exemption from a Food and Drug Administration (FDA), Investigational Device Exemption (IDE) because it is a, “Legally marketed device used in accordance with its labeling.” Please refer to the approved FDA IDE approval letter from OCR submitted with this protocol.

5.1 Detailed Product Description of Equipment

Figure 1: Transesophageal Echocardiography Probe

Figure 1: This image is a photograph of a Philips transesophageal echocardiography (TEE), ultrasound probe. During cardiac surgeries, this probe is passed through the

Clinical Study Number:	NCT06154265	Document Title:	10/24/2024	Page 10 of 36
		Default vs As-Needed Intraoperative Transesophageal Echocardiography (TEE) in Low-Risk Isolated Coronary Artery Bypass Graft (CABG) Surgery: A Randomized Controlled Trial		

patients oropharynx and advanced into the esophagus and/or stomach to acquire real-time, ultrasound-based, cardiac images during surgery.
<https://www.usa.philips.com/healthcare/resources/feature-detail/ultrasound-tee-imaging>

Clinical Study Number:	NCT06154265	Document Title:	10/24/2024	Page 11 of 36
		Default vs As-Needed Intraoperative Transesophageal Echocardiography (TEE) in Low-Risk Isolated Coronary Artery Bypass Graft (CABG) Surgery: A Randomized Controlled Trial		

6 Study Objectives and Purpose

The overall objective of this RCT is feasibility testing. To accomplish this, we will randomize eligible isolated CABG surgery patients to receive either default (i.e., obligatory) vs as-needed (i.e. backup) intraoperative TEE. Enrolled subjects will be randomized after induction of anesthesia. Trial outcomes will include subject recruitment, overall rate of TEE performed in the as-needed trial arm, and clinical outcomes.

6.1 Primary Objective(s)

- Recruitment feasibility assessment as measured by an absolute recruitment. Absolute recruitment will be defined as the number of successfully enrolled participants divided by the total number of screened participants.
- Calculate the rate of TEE performed among participants randomized to as-needed TEE trial arm.

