8.2 Screening

- The cardiac surgery outpatient office will serve as the primary location for pre-screening potentially eligible participants but inpatients who meet inclusion criteria will also be eligible. Screening of the clinic schedule or the inpatient cardiac surgical census will identify potential patient subjects that meet study entry criteria. Eligible patients will be approached after it is determined that CABG is indicated for standard of care. Patients will not be approached for enrollment on the day of surgery to allow adequate time for the patient to consider the risks and benefits to participation.
- Patient subjects will be invited to participate in trial at after completing their pre-operative surgical office visit at a UPenn cardiac surgery clinic or following admission to the hospital. Time allotted for patient subject enrollment in the study will be approximately 30-45 minutes in order to adequately allow for a comprehensive discussion on the risks/benefits to patient participation, and to answer any questions that might arise during the consenting process. If English is not the subject's first language an interpreter will be used to facilitate the informed consent process in the subject's native language. The subject will be provided the cellphone number of the PI or their designee and informed that they can call the PI or designee with any questions.

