8.3.3 Financial Compensation for Trial Participation

- Patients will not be financially compensated for participation in this trial.

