10.3 Sample Size and Power Determination

- To account for screen failures (i.e., exclusions after enrollment), we are planning to obtain informed consent for up to 75 patients to ensure we achieve our enrollment goal of 22 patients randomized to each trial arm.

Clinical Study Number:	NCT06154265	Document Title:	10/24/2024	Page 18 of 36
		Default vs As-Needed Intraoperative Transesophageal Echocardiography (TEE) in Low-Risk Isolated Coronary Artery Bypass Graft (CABG) Surgery: A Randomized Controlled Trial		

11 Risk and Benefit Analysis

The standard-of-care intraoperative TEE device has passed quality assurance testing according to international regulatory guidelines. But specific to low-risk, isolated CABG surgery, the risk vs benefit profile for intraoperative TEE as an invasive hemodynamic monitoring device is currently unknown. Consequently, given that neither arm of the trial will be deprived of intraoperative TEE, the benefits of a greater understanding of who, when, and why intraoperative TEE should be used in isolated CABG surgery outweigh the risks in participating in a trial randomizing patients to two standard-of-care trial arms. The concrete risks associated with RCT participation and the steps put in place to mitigate these risks will be reviewed.

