11.2 Risk Minimization Actions

Risk to trial subjects will be minimized by: (a) training of all staff directly-involved in research activities in the ethical conduct of research; (b) strict protection of confidentiality through detailed standard operating procedures and on-site monitoring; (c) careful handling of sensitive data, including procedures and processes in place to ensure data are securely stored and transferred.

While the potential risks to subjects are low overall, any harm will be reported to the principal investigator (PI) immediately, and any serious event will be reported to both the data safety and monitoring board and the University of Pennsylvania IRB within 48 hours of its occurrence.

- The following are the protections against the trial risks (itemized above in section 11.1 above):
 - (1) Risk of harm from the TEE probe itself: Patients will be (if randomized to the default trial arm) and may be (if randomized to the as-needed trial arm) exposed to the gastroesophageal clinical risks associated with use of the TEE probe itself. However, the current standard of care for isolated CABG surgery at PPMC involves the obligatory placement of an intraoperative TEE to be used continuously throughout surgery unless clinically contraindicated. Consequently, patients enrolled in this trial will not be exposed to undue risk from placement of the TEE probe beyond that of the standard of care. Moreover, patients randomized to the as-needed TEE trial arm may be protected against suffering the gastroesophageal complications related to the TEE procedure itself if they undergo surgery without the use of TEE.
 - (2) Risk of harm from the absence of continuous TEE monitoring during isolated CABG surgery: Patients randomized to the as-needed intraoperative TEE arm may be exposed to consequences associated with delayed diagnoses of hemodynamic instability (e.g. EKG changes indicating impending myocardial ischemia and need for TEE assessment). To protect against this risk of delayed diagnosis of myocardial ischemia (or other unforeseen intraoperative complications), in consultation with cardiac surgeon collaborators, we have outlined strict inclusion and exclusion criteria to limit trial participation to the lowest-risk, normal ejection fraction, isolated CABG surgical patient population. Additionally, we will randomize patients after induction of anesthesia to ensure that only hemodynamically stable patients are enrolled in this trial.

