15.4 Privacy

Patients will be consented one-on-one, in a private office room if consented in the cardiac surgical outpatient clinic or their private bay in the preoperative holding area. Either a door will be shut or a curtain will be drawn for the consenting process to maintain patient subject privacy.

16 Publication Policy

In accordance with the NIH Public Access Policy and Federal law, an electronic version of the final, peer reviewed, publication(s) resulting from this trial will be submitted to PMC to be made publicly available no later than 12 months after the official date of publication.

17 Ethical Considerations

This study is conducted in accordance with the ethical principles that have their origin in the Declaration of Helsinki. The protocol and all study materials are to be reviewed by an Institutional Review Board (IRB)/Ethics Committee (EC), prior to enrollment of any subject. Any additional requirements imposed by the IRB/EC shall be followed. Any amendments to the protocol must be reviewed and approved by

Clinical Study Number:	NCT06154265	Document Title:	10/24/2024	Page 24 of 36
		Default vs As-Needed Intraoperative Transesophageal Echocardiography (TEE) in Low-Risk Isolated Coronary Artery Bypass Graft (CABG) Surgery: A Randomized Controlled Trial		

the NIH, and subsequently, by the designated IRB/EC, according to the approval committee's requirements.

Only authorized personnel associated with the conduct and/or review of the study and the resultant data shall have access to information that links subject identifiers to the corresponding assigned study code. Disclosure of subject information to personnel other than those permitted by the NIH, NHLBI, its designees or representatives, or appropriate regulatory agencies is prohibited.

Clinical Study Number:	NCT06154265	Document Title:	10/24/2024	Page 25 of 36
		Default vs As-Needed Intraoperative Transesophageal Echocardiography (TEE) in Low-Risk Isolated Coronary Artery Bypass Graft (CABG) Surgery: A Randomized Controlled Trial		

18 References

1. [name] EJ, Neuman MD, Fleisher LA, et al.: Transesophageal echocardiography, mortality, and length of hospitalization after cardiac valve surgery. *Journal of the American Society of Echocardiography*. 33:756-762. e751, 2020.

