19.2 Recruitment and Retention Plan

19.2.1 Recruitment Plan

- Recruitment for the randomized controlled trial (RCT) will occur through the Penn Presbyterian Medical Center (PPMC) cardiac surgery clinic of the University of Pennsylvania Health System. Within our Institutional Review Board (IRB) protocol, we will request permission to access clinic and surgical schedules of potential isolated coronary artery bypass graft (CABG) patients in order to identify potential RCT subjects that meet inclusion and exclusion criteria for enrollment in the trial. Once a potential subject has been identified, he or she will be approached in-person, pre-procedure. After a brief introduction, either the research assistant (RA) or the principal investigator (PI) will approach these patient participants and ask if they would be interested in hearing about the trial. If they agree, the RA or PI will ask a series of additional screening questions to confirm that the patient meets eligibility criteria. If the patient is deemed eligible and expresses interest in learning more about the study, the RA or PI will review the intent of the study, present the current data regarding risks and benefits to using intraoperative transesophageal echocardiography (TEE) during isolated CABG surgery. Once the patient agrees to participate, the RA or PI will complete the enrollment process by providing an information packet, collecting basic demographic and health data, reviewing study timeline and protocols, and obtaining written informed consent that confirms the study subjects' agreement to participate in the RCT as specified in the trial protocol and the subjects' permission to allow the research team to access electronic medical records. Patients will receive an incentive for completing all phases of the study. The trial inclusion and exclusion criteria for subject participation listed in the above-protocol will be confirmed and finalized with [name] prior to initiation of recruitment.

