19.2.1.1 Estimated Rates of RCT Enrollment

- We will recruit up to 75 isolated CABG surgery patients who present to the cardiac surgery clinic(s) at either PPMC or the Hospital of the University of Pennsylvania. The Division of Cardiovascular Surgery, within the University of Pennsylvania Health System is the largest cardiac surgery division in the State of Pennsylvania and receives over 250 isolated CABG referrals per year. This breaks down to approximately 20 patients per month. Assuming half of these patients meet inclusion criteria (i.e. 10 potential subjects per month), to meet our sample size of 22 isolated CABG surgery patients in year, we would need a 20% participation rate over 12 months; equating to approximately 2 – 3 study subjects per month. Although we do not anticipate difficulty in recruitment, if we are unable to achieve our

Clinical Study Number:	NCT06154265	Document Title:	10/24/2024	Page 33 of 36
		Default vs As-Needed Intraoperative Transesophageal Echocardiography (TEE) in Low-Risk Isolated Coronary Artery Bypass Graft (CABG) Surgery: A Randomized Controlled Trial		

projected sample size goal within one year, we will extend the recruitment period six months.

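### The numerator of the primary recruitment rate is contradictory: enrolled means consented in some sections and randomized in others, and the screened denominator is not defined

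*Combined protocol and SAP*

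**What the plan says.** The Protocol Synopsis and section 6.1 give the same ratio: "Absolute recruitment will be defined as the number of successfully enrolled participants divided by the total number of screened participants". Section 10.1 lists the endpoint by name without a formula. No section defines either term for this purpose.

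**Enrolled as consented, or as a step before randomization**
- Section 6 has subjects who are already enrolled being randomized after induction.
- Section 8.3.2 treats consent and enrollment as one act by the investigator or coordinator.
- Section 19.2.1 describes an enrollment process that ends with written consent.
- Section 10.3 opens with "To account for screen failures (i.e., exclusions after enrollment), we are planning to obtain informed consent for up to 75 patients", so a patient can be excluded after being enrolled.

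**Enrolled as randomized**
- The same sentence in section 10.3 ends with an enrollment goal counted in randomized patients, 22 per arm.
- Section 11.2 says "we will randomize patients after induction of anesthesia to ensure that only hemodynamically stable patients are enrolled in this trial".

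**Screened.** Section 8.2 starts screening from the clinic schedule or the inpatient surgical census. Section 6.3 makes the investigator responsible for confirming that screened subjects are eligible.

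**Planning figures.** Section 19.2.1.1 gives over 250 isolated CABG referrals a year for the division, assumes half are eligible (10 a month), and for a sample size of 22 says "we would need a 20% participation rate over 12 months". Section 19.2.1.2 undertakes to document recruitment among eligible patients to inform the future trial.

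**The concern.** Feasibility is the overall objective, and this ratio is one of only two primary endpoints. The two senses of enrolled are separated by a real event. Exclusion criterion 14 (instability after induction) can be judged only after consent and before randomization, and section 8.4.1 removes such patients at that point. Under the consent sense these losses, and any other loss between consent and the operating room, never reach the headline rate. Under the randomized sense they do.

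The denominator adds a second difficulty. A count taken from a schedule or census includes patients who are ineligible on their chart as well as eligible patients who decline. A low ratio could then reflect narrow criteria, refusal or post-induction exclusion, and each calls for a different response in a multicenter trial. If the definitions are chosen once the counts are known, the result can be chosen with them.

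**Working it through.** **Inputs**
- Referrals: 250 a year, about 20 a month (section 19.2.1.1; the text says over 250, division-wide).
- Eligible: half, so 10 a month, giving 120 or 125 a year (section 19.2.1.1).
- Consents: at most 75 (sections 10.3 and 19.2.1.1).
- Randomized: 22 per arm, 2 × 22 = 44 (section 10.3). Sections 19.2.1.1 and 19.5.2 instead give 22 in all.

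**Step 1: reproduce the plan's own figure.** Participation needed = target / eligible in 12 months.
- Target 22: 22/120 = 18.3%, or 22/125 = 17.6%. In reverse, 20% × 120 = 24 patients, or 2 a month. The stated 20% reproduces.
- Target 44: 44/120 = 36.7%, or 44/125 = 35.2%. The stated 20% does not reproduce.

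The 20% therefore belongs to a total of 22 and not to 22 per arm.

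**Step 2: the numerator alone.** Hold the denominator at the section 6.1 wording, and assume that all 250 referrals are screened within 12 months, 75 consent and 44 are randomized.
- Enrolled = randomized: 44/250 = 17.6%.
- Enrolled = consented: 75/250 = 30.0%.
- Ratio of the two: 75/44 = 1.7.

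The ratio does not depend on how many are screened, because the denominator cancels. It depends only on how many consented patients fail to reach randomization.

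**Step 3: what the consent reading leaves out.** 75 − 44 = 31, and 31/75 = 41%. This is an upper limit, because 75 is a ceiling.

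**Step 4: sensitivity to the assumptions**
- Recruitment over 18 months (the six-month extension in section 19.2.1.1), same counts: 250 × 1.5 = 375 screened; 44/375 = 11.7% against 75/375 = 20.0%.
- Total of 22 randomized: 22/250 = 8.8%.
- Referrals at 20 a month: 44/240 = 18.3% against 75/240 = 31.2%.

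The level of the rate moves with each assumption. The gap between the readings remains unless nobody is lost after consent. I attach no confidence intervals because these are planning counts, not data.

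**The case against.** The rate is descriptive, with no test, threshold or power calculation attached (section 19.5.2), so one could say that a flow diagram in the report would settle the matter. A diagram would show the counts, but it would not say which of them is the primary endpoint. The protocol gives conflicting answers to that, so the objection lowers the stakes without removing the problem.

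Several stronger readings are tempting, and the documents do not support them:
- *That identical data could give anything from 18% to 60%.* The upper figure is 75/125, which replaces screened patients with eligible ones. Section 6.3 can be read that way and section 19.2.1.1 plans that way, but section 6.1 says screened. On its stated denominator the illustration runs from 17.6% to 30.0%.
- *That the plan expects to lose 41% after consent.* Section 10.3 gives up to 75 as a ceiling to secure the target. No section forecasts a loss.
- *That the endpoint is judged against a 20% benchmark on a different scale.* The 20% is an accrual assumption, and no section compares the endpoint with it.
- *That the trial could not separate eligibility from refusal.* Section 19.2.1.2 already intends rates among eligible patients. What is missing is a formal link to the endpoint.

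It is also fair to say that 250 is a division-wide referral count, while section 9 names a single site. The true screened number is unknown.

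**Conclusion.** The contradiction stands. It is a conflict within a primary endpoint and not merely missing detail, since one sentence of section 10.3 carries both meanings. Under the assumptions of step 2 the choice of numerator moves the rate by 30.0 − 17.6 = 12.4 percentage points, and the consent reading would conceal up to 31 of 75 losses. The sizes are illustrative; the contradiction does not depend on them. The merging of ineligibility with refusal is a real limit on interpretation, but reporting the steps resolves it and a new primary denominator is not required.

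Two side points concern the conditions under which the rate is measured, not the counts that enter it. Section 8.3.3 says "Patients will not be financially compensated for participation in this trial" while section 19.2.1 says "Patients will receive an incentive for completing all phases of the study". A non-financial incentive would reconcile them, but the text does not say that. Section 8.2 says "Patients will not be approached for enrollment on the day of surgery", while section 15.4 allows consent in the clinic "or their private bay in the preoperative holding area", a setting that suggests the day of surgery without stating it.

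**What to change.** 1. In the Synopsis and section 6.1, define successfully enrolled as randomized. Align sections 6, 8.3.2, 10.3 and 19.2.1, using consented where consent is meant.
2. Define screened as all patients reviewed on the clinic schedule or inpatient census, and keep randomized/screened as the primary rate. Making randomized/eligible primary instead is a trade-off that the ambiguity does not force.
3. Report the sequence screened > eligible on preoperative criteria > approached > consented > passed the post-induction check > randomized. Give each step an exact 95% CI, and name randomized/eligible as a supporting rate. The preoperative qualifier is needed because criterion 14 is assessed after induction.
4. Reconcile the total of 22 (sections 19.2.1.1 and 19.5.2) with 22 per arm (section 10.3), and restate the participation figure to match: 20% fits a total of 22, while 44 needs about 35% to 37%.
5. Separately, reconcile section 8.3.3 with 19.2.1 on the incentive, and section 8.2 with 15.4 on consent in the holding area.

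The cost is rewording in the sections named and a screening-log template, with no new visits or procedures. The log has to be kept prospectively, because counts of approaches and refusals may be hard to recover later. The headline rate will be somewhat lower than one that counts consents.
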